3.2 Secondary objectives

- 1. To determine the overall survival of patients treated with Axitinib
- 2. To determine the progression free survival of patients treated with Axitinib
- 3. To determine the disease control rate at 16 weeks and response rate as defined by Choi Criteria
- 4. To determine the duration of response (as defined by Choi Criteria) of patients treated with Axitinib
- 5. To assess the toxicities associated with the treatment of Axitinib of patients treated with Axitinib

4. STUDY DESIGN:

This study will be a prospective, single-institution, single-arm phase II study of Axitinib in patients with unresectable recurrent and metastatic head and neck squamous cell carcinoma with ECOG performance status 0-2, for recurrent or metastatic head and neck cancer. The subjects will be started on treatment with 5 mg of Axitinib twice a day continuously, with subsequent dose escalation to 7 mg and then 10 mg twice a day in the absence of grade 2 or worse toxicities. This will be followed by clinical and/or radiologic response assessment after 8 weeks and subsequently every 2 months until disease progression (defined per Choi criteria, or obvious progression on clinical or laryngoscopic/endoscopic exam) or intolerable toxicity (defined as below). Patients with confirmed progressive disease who, in the investigator's opinion, continue to receive benefit from Axitinib treatment and who meet the criteria for treatment may continue to receive treatment as described in Section 8.3. Axitinib should be discontinued if there is further evidence of progression defined as an additional 10% or greater increase in tumor burden volume from time of initial progression (including all target lesions and new measurable lesions).

During treatment on this protocol, all patients will be evaluated for safety as detailed below.

5. STUDY POPULATION:

5.1. Stage:

Unresectable, recurrent or metastatic squamous cell carcinoma of head and neck.

5.2. Inclusion Criteria:

1. Histologically documented squamous cell head and neck cancer with or without metastases, not amenable to curative treatment; or the patient has documented refusal of curative treatment.

2. Presence of measurable disease by CT scan or

a. for cutaneous squamous cell carcinoma not present on CT imaging but present on physical exam with lesion(s) greater than >/= 10mm

b. patients with non-target lesions are permissible per PI discretion

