6.2. Trial procedures

During treatment on this protocol, all patients will be followed and monitored as follows:

Table 6. Trial Procedures.

		Cycle						Following	Following completion	al ¹¹
D 1	D	l,	1		2	4	0	each	of even	viv
Required	Pre-	Day		2	3	4	8	cycle thru	numbered	Sur
studies	therapy ¹²		week	weeks	weeks	weeks	weeks	12 cycles ¹	cycles	01
Clinic visit	X	X		X		X	X	X	X	
H&P	X	X^{10}		Х		X	X	Х	Х	
Vital signs and PS	Х	Х		Х		Х	Х	Х	Х	
PTT, PT, INR	Х									
CBC, Diff, platelets	Х	X ⁹		Х		Х	Х	Х	Х	
Comprehensive Panel, Mg ²	X ³	X ⁹		Х		Х	Х	Х	Х	
Urine dip ³	Х					Х	Х	Х	Х	
TSH, free T4 ⁴	Х	X ^{9,}		Х		Х			Х	
Clinical										
toxicity				Х		Х	Х	Х	Х	
assessment										
Radiologic										
imaging for	v						v		\mathbf{v}	
tumor	Λ						Λ		Λ	
measurement ⁵										
Pregnancy Test ⁶		X ⁹								
Informed	v									
Consent	Λ									
Planned dose				v	v					
escalation ⁷				Λ	Λ					
Telephone										
assessment of			Х		Х					
toxicities ⁸										
Survival										v
Monitoring										Λ

- 1- Following completion of 12 cycles, assessments will be obtained every 8 weeks.
- 2- Comprehensive Panel includes Basic Panel (Na, K, Cl, CO2, BUN, Cr, Gluc), AST/SGOT, ALT/SGPT, Alk Phos, T.bili, Alb, Ca, Total Protein. Also will obtain magnesium.
- 3- Urine dipstick may be done in clinic or lab.
- 4- Serum or plasma Thyroid Function Tests (Free T4 and TSH) should be performed within 14 days of starting treatment. Subsequently, TSH should be done every 2 weeks X 2, then following completion of even numbered cycles of chemotherapy.

- 5- Radiologic imaging of the areas involved with recurrent/metastatic disease, such as the neck, chest, or other areas if needed because of the location of the metastatic disease; baseline within 28 days prior to treatment. On study assessments, may be within +/- 2 weeks. Imaging will be interpreted by Choi Criteria, interpretation to be performed by centralized UMCC Tumor Response and Assessment Core (TRAC).
- 6- Pregnancy test (urine or serum) will be performed for women of childbearing age within 3 days before first dose of Axitinib and if clinical concern for pregnancy arises.
- 7- Dose escalation is planned at 2 weeks (to 7 mg BID) and 3 weeks (to 10 mg BID), in the absence of toxicities grade 2 or greater. Dose escalation may be resumed after 1 week if all toxicities have diminished to grade 1 or less (see below), and measures have been taken to reasonably prevent recurrence of these toxicities with the higher dose.

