For statistical analysis that include the investigator-assessed progression date, subjects who continue treatment beyond investigator-assessed, Choi Response defined progression will be considered to have investigator-assessed progressive disease at the time of the initial progression event.

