Overall and progression-free survival rates at 2, 4 and 6 months will be reported along with 95% confidence intervals based on the binomial distribution. Kaplan-Meier methods will also be conducted to estimate these rates and the medians of PFS and overall survival (OS) of the 37 evaluable patients, with a corresponding standard error estimate based on Greenwood's formula (53).

Among this cohort of patients, progression will be determined based on Choi critieria.

- To determine the response.

The best overall response rate will be determined for each evaluable patient at 8 and 16 weeks following the start of Axitinib. The proportion of evaluable patients who have an objective response (complete or partial) and stable disease will be calculated, and a 95% exact binomial confidence interval will be determined.

- To determine the toxicity profile of this treatment regimen.

The proportion of treated patients experiencing any clinically significant (Grade 3 or worse) toxicity will be determined, with a 95% exact binomial confidence interval; specific toxicities of all grades will be tabulated.

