14. DATA ANALYSIS

14.1. Analysis of Overall Survival

Overall survival will be determined from the date of treatment initiation to date of death from any cause. For the primary endpoint, patients that are alive at 6 months following the initiation of study treatment will be considered successful. All other patients will be considered unsuccessful. Patients will be considered evaluable for the primary endpoint if they receive any dose of Axitinib. For the primary endpoint we anticipate no missing data and will test whether the proportion alive at 6 months is greater than the historical rate of 50% with an upper tailed test of binomial proportion.

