14.3. Efficacy Analysis

Efficacy analysis will include Progression-free survival (PFS), Overall response rate (ORR), including complete (CR) and partial response (PR), stable disease, disease control rate (CR+PR+stable disease) at 16 weeks, along with overall survival (OS).

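### Does naming only the Choi criteria in Section 13.4 leave progression-free survival (PFS) wrongly or unusably defined?

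*Combined protocol and SAP*

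**What the plan says.** PFS is the second secondary objective (Section 3.2). Section 14.3 lists it among the efficacy analyses without defining it. Section 13.4 gives the analysis: "Overall and progression-free survival rates at 2, 4 and 6 months will be reported along with 95% confidence intervals based on the binomial distribution". It adds Kaplan-Meier estimates and medians with Greenwood standard errors, and on progression it says: "Among this cohort of patients, progression will be determined based on Choi critieria".

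Four other places bear on the definition.

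- **Section 4** follows patients until disease progression, "defined per Choi criteria, or obvious progression on clinical or laryngoscopic/endoscopic exam". The assessment that leads there may rest on examination, imaging or both: "This will be followed by clinical and/or radiologic response assessment after 8 weeks".
- **Section 6.2, footnote 5**, with Sections 7.1 and 9, gives the Choi reading to the institution's central imaging core (TRAC).
- **Section 8.3** covers patients treated beyond progression. For analyses that use the investigator's progression date, they "will be considered to have investigator-assessed progressive disease at the time of the initial progression event".
- **Sections 13.1 and 14.1** define overall survival in full: "Overall survival will be determined from the date of treatment initiation to date of death from any cause". PFS has no matching sentence.

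**The concern.** Read literally, Section 13.4 and Section 4 give different answers for a patient whose tumour has plainly grown on examination but who has no qualifying scan. Under Section 4 the patient has progressed. Under Section 13.4 the patient might stay progression-free or be censored. The literal reading can only leave PFS equal or raise it, so any bias would run in one direction.

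The missing pieces add to this. Overall survival has a start date and an event, while PFS has neither in writing, nor a rule for deaths or censoring. The investigator and the imaging core might date the same progression differently, and nothing says which date prevails. The binomial rates at 2, 4 and 6 months have no stated place for a patient whose status is unknown.

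Section 1.2 argues that PFS was underestimated in the previous study, where the 6-month figure was 27%. If readers set the new figure beside that one, part of any difference could come from which events were counted.

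**Working it through.** **1. The plan's own figure.** Section 13.2 states 37 patients, 80% power, 70% against 50% alive at 6 months, type I error 5%, upper-tailed binomial test. The exact rule is at least 24 of 37 alive.

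- P(X ≥ 24 | n = 37, p = 0.50) = 0.0494
- P(X ≥ 24 | n = 37, p = 0.70) = 0.807

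The stated size reproduces. It depends on deaths alone, so no choice about PFS can alter it.

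**2. The passages side by side.**

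- *Choi and clinical progression.* Section 13.4 does not say that Choi is the only route. It refers to this cohort, and Section 1.2 presents the trial as repeating the previous treatment plan with Choi as the response criteria, plus continuation for clinical benefit. The previous study used RECIST v1.0. Section 13.4 therefore names the imaging standard, and Section 4 adds what is evident on examination. The two can be applied together.
- *What Choi as adopted already covers.* Section 9 counts new lesions as progression and allows lesions measurable only on examination to be judged by size. It withholds stable disease when symptoms worsen because of the tumour, and partial response when non-measurable disease has obviously grown. These last two rules do not make such a patient a progressor in terms, but they make it hard to call the patient progression-free.
- *Death.* Section 13.4 reports PFS beside overall survival as a survival rate. A patient who has died is not surviving without progression, and nothing suggests that deaths would be censored.
- *Start date.* Overall survival runs from treatment initiation, and Section 13.4 times response from the start of Axitinib. No other origin is in view.
- *Whose date.* The Section 8.3 rule is conditional on an analysis using the investigator's date. It fixes which event counts and does not take the reading from the imaging core. This is an unstated choice rather than a contradiction.
- *Unknown status at a landmark.* For the primary endpoint, Section 13.1 counts everyone not alive at 6 months as unsuccessful. Applying the same rule to the PFS rates is an obvious course.

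**3. Possible size.** The number of patients progressing on examination alone is not given. For illustration, assume that the earlier 27% holds here under the Section 4 definition.

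- Baseline: 0.27 × 37 = 9.99, so 10/37 = 27.0%, exact 95% interval 13.8 to 44.1%.
- Let k of the 27 events be progressions on examination only, in patients alive without Choi progression at 6 months.
- Kept progression-free, the rate is (10 + k)/37.
- Censored, with no other censoring, the Kaplan-Meier estimate lies between 10/(37 − k), all censored earliest, and (10 + k)/37, all censored latest.

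| k | Censored earliest | Kept progression-free, or censored latest |
|---|---|---|
| 0 | 27.0% | 27.0% |
| 1 | 10/36 = 27.8% (+0.8) | 11/37 = 29.7% (+2.7) |
| 4 | 10/33 = 30.3% (+3.3) | 14/37 = 37.8% (+10.8) |

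A rise of 10 points needs 4 patients if all are kept progression-free (3 give 13/37 = 35.1%, or +8.1). It needs 10 if all are censored at entry (10/27 = 37.0%). To pass the upper limit of 44.1%, 7 must be kept progression-free: 16/37 = 43.2% and 17/37 = 45.9%. That would be 7/27 = 26% of all events.

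**The case for a change.** The best case for a change is that convention does not settle everything. It says that death is a PFS event, but not whether progression seen only on examination counts, nor whether the investigator's or the imaging core's date is used. Nor does it settle how a patient who leaves for curative surgery or chemoradiation (Section 10, item 7) is handled. Patients are examined at every visit but imaged only about every 8 weeks, so examination may show progression first. The trial is open-label with one arm, and a definition settled after the data are seen invites a favourable choice. Writing it down would take a paragraph.

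Much of this stands as description. The PFS definition is incomplete, and a report should state the one used. It does not show that the plan is wrong. Either Choi-only PFS or Choi plus clinical progression would be acceptable if stated, so the main question is a choice between two defensible definitions. The comparison with 27% is not planned anywhere. That figure came from 30 evaluable patients assessed by RECIST v1.0, and the documents do not show its event list, so even the direction of a cross-study bias cannot be established.

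**Conclusion.** No change to the plan follows. This is missing detail on a descriptive secondary endpoint, and an analyst can fill it sensibly from the plan itself:

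- time from treatment initiation;
- Choi progression or the clinical progression named in Section 4, whichever comes first, or death;
- the initial event as the date;
- censoring at the last progression-free assessment.

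The effect may be zero. Under the assumed 27%, one affected patient moves 6-month PFS by 0.8 to 2.7 points and four by 3.3 to 10.8 points, against an interval of 13.8 to 44.1%. A larger distortion would need about a quarter of all events to be seen on examination only, in patients alive at 6 months without Choi progression and all kept progression-free. The documents neither support nor exclude that. The primary survival test, its size and its power are unaffected. The conclusion rests on PFS remaining descriptive, as planned, with no formal comparison against the previous study.

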Figure 3: Kaplan-Meier Analysis of Overall Survival in UMCC 2011.53

We strongly believe that Axitinib is a promising therapeutic, merits further consideration as a novel therapeutic in R/M HNSCC, and that the results of the UMCC 2011.53 are misleading for several reasons. First, we note the impressive overall survival (median 10.9 months) observed in the heavily pretreated UMCC 2011.53 population with a low incidence of grade 3 or 4 toxicities. The current first line therapy in newly diagnosed R/M HNSCC is a triplet therapy (the 'EXTREME' regimen) consisting of Cetuximab, Cisplatin, and 5-flurouracil which has been shown to be associated with a median OS of 10.1 months with relatively high rate of grade 3 or 4 toxicities(82%) (9). In studies of patients failing first line therapy, median overall survival (OS) is typically on the order of 4-8 months. Ninety percent of the patients in our study had previous lines of therapy in the R/M setting suggestive of significant survival benefit with Axitinib therapy.

We believe that the reason UMCC 2011.53 demonstrated impressive OS but did not demonstrate improvement in PFS (and hence was stopped for futility) is that tumor response to therapy (swelling, cystic attenuation) was registered as progression by RECIST v1.0. Similar results regarding responses have been described with tyrosine kinase inhibitors, most notably in advanced gastrointestinal stromal tumors (GISTs). To account for these alternate radiologic changes, an alternate set of response criteria have been proposed for patients treated with tyrosine kinase inhibitors known as the Choi Criteria (Table 9). In one study, it was demonstrated that radiologic changes defined by Choi Criteria correlated with patient directed endpoints (PFS, DSS, OS) whereas RECIST did not capture these correlations.

Table 5: Definition of Choi Criteria

Axitinib In Head And Neck Cancer -- Protocol For A Phase II Study

Response	Definition
CR	Disappearance of all lesions
	No new lesions
PR	A decrease in size* of \geq 10% or a decrease in tumor density (HU) \geq 15% on CT
	No new lesions
	No obvious progression of nonmeasurable disease
SD	Does not meet the criteria for CR, PR, or PD
	No symptomatic deterioration attributed to tumor progression
PD	An increase in tumor size of \geq 10% and does not meet criteria of PR by tumor density (HU) on CT
	New lesions
	New intratumoral nodules or increase in the size of the existing intratumoral nodules

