Abbreviations: CR, complete response; PR, partial response; HU, Hounsfield unit; CT, computed tomography; SD, stable disease; PD, progression of disease; RECIST, Response Evaluation Criteria in Solid Tumors. *The sum of longest diameters of target lesions as defined in RECIST.¹⁰

We have reviewed all the radiographic images for all of the patients on UMCC 2011.53 by Choi Criteria as a hypothesis generating exploratory analysis. Of note, only 29/30 patients evaluable for response had imaging for which the Choi Criteria could be applied. In addition, imaging was not optimized for interpreting images with alternate radiologic criteria. Preliminary exploratory analyses demonstrate that (23/29) 65% of patients enrolled on UMCC 2011.53 had a response (PR) by Choi Criteria with an additional 2 patients achieving stable disease (6.9%) (Table 4).

Furthermore, overall survival was found to be significantly improved in patients with a response by Choi Criteria versus non-responders (KM estimate of OS (95% CI): 13.2(10.3,18.7) months versus 5.1 (2.5, 8.8) months) (Figure 5). Further analyses was limited as treatment decisions were made off of RECIST but predicted survival at 12 months was 63% (95% CI: 38-80%) in patients with a response versus 20% (95% CI: 3-47%) in non-responders.

Figure 4: Kaplan-Meier Analysis of Overall Survival by Choi Response in UMCC 2011.53

Given the existing literature in other malignancies treated with tyrosine kinase inhibitors, mechanism of action of Axitinib, and our exploratory analysis in evaluating response with alternate criteria we feel that use of Choi Criteria for assessment for tumor response and treatment decisions is more appropriate for ongoing R/M HNSCC trials. We believe that improvements in survival endpoints (ie PFS) may be underestimated in the existing UMCC 2011.53 cohort as Axitinib was stopped in the setting of a RECIST progression despite Choi response.

Therefore, we propose a trial examining the use of Axitinib in R/M HNSCC using the Choi Criteria for response assessment. We would power this cohort to detect a 20% improvement in 6 month overall survival compared to historical data (from 50% to 70% at 6 months). This cohort would consist of 37 patients and treatment plan would be identical to the previous UMCC 2011.53 protocol with the exception that Choi criteria would be used to evaluate response. In addition, treatment with Axitinib would be continued if patients were felt to be deriving clinical benefit.

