The response to treatment will be assessed clinically at each visit, as well as by appropriate radiologic imaging, starting at 8 weeks +/- 2 weeks and then at 8-week intervals, +/- 2 weeks. Tumor response to therapy will be interpreted by Choi Criteria with interpretation performed by UMCC Tumor Response and Assessment Core. Patients will be taken off trial for significant side effects, per patient preference, or for noncompliance with treatment plan. Beyond progression, survival will be assessed every 12 weeks. Patients will also be followed for 28 days after cessation of study participation for safety monitoring. Patients with confirmed progressive disease who, in the investigator's opinion, continue to receive benefit from Axitinib treatment and who meet the criteria for treatment may continue to receive treatment as described in Section 8.3. Axitinib should be discontinued if there is further evidence of progression defined as an additional 10% or greater increase in tumor burden volume from time of initial progression (including all target lesions and new measurable lesions).

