9. RESPONSE CRITERIA

The Choi Criteria will be used to assess tumor response to therapy. Interpretation will be performed by centralized UMCC Tumor Response and Assessment Core (TRAC). If density measurements are not available and cannot be accurately measured by photography or imaging, response can be dictated by measurement alone (i.e.for cutaneous squamous cell carcinomas that are not visualized on CT scan but are measurable on physical exam only). Non-target lesions are also permissible in which case overall assessment would be limited to complete response, stable disease, and progressive disease.

Complete Response:

- Disappearance of all lesions
- No new lesions

Partial Response:

- A decrease in size¹ of $\ge 10\%$ or a decrease in tumor density (HU) $\ge 15\%$ on CT
- No new lesions
- No obvious progression of non-measurable disease

Stable Disease

- Does not meet the criteria for CR, PR, or PD
- No symptomatic deterioration attributed to tumor progression

Progressive Disease

- An increase in tumor size of \geq 10% and dose not meet criteria of PR by tumor density (HU) on CT
- New lesions
- New intratumoral nodules or increase in the size of the existing intratumoral nodules
- ¹⁻ The sum of longest diameters of target lesions as defined in RECIST

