10. CRITERIA FOR DISCONTINUATION OF TREATMENT

- 1. Unacceptable toxicity.
- 2. Intercurrent illness, which prevents further administration of treatment.
- 3. Patient preference.
- 4. Confirmed PD and Investigator determination that the patient is no longer benefiting from treatment with Axitinib (per section 8.3)
- 5. Treatment delays due to drug-related toxicity > 2 weeks.
- 6. Non-compliance with treatment.

7. If the disease becomes amenable to resection or (chemo) radiation with curative intent as a result of Axitinib treatment, Axitinib will be stopped, and the alternative treatment instituted that would offer the best chance of cure for the patient. Such patients will be included in safety and efficacy analysis.

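### Choi response is counted without a confirming scan, so some stable patients may be counted as responders through measurement error; the size is unknown, and a confirmed rate should be shown beside the planned one

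*Combined protocol and SAP*

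**What the plan says.** - **Definition.** Section 9 (and Table 5 in section 1.2) grants partial response (PR) if either the sum of diameters falls by at least 10% or CT density falls by at least 15%. The further conditions are no new lesions and "No obvious progression of non-measurable disease". No confirming scan is listed for complete response (CR) or PR.
- **Analysis.** Section 13.4: "The best overall response rate will be determined for each evaluable patient at 8 and 16 weeks following the start of Axitinib". The proportion with response is then reported with an exact 95% confidence interval. No null rate or test is given.
- **Schedule.** Section 7.1 plans imaging "starting at 8 weeks +/- 2 weeks and then at 8-week intervals, +/- 2 weeks", so a week-24 scan is already scheduled for patients still being imaged.
- **Reading.** Section 9: "Interpretation will be performed by centralized UMCC Tumor Response and Assessment Core (TRAC)".
- **Confirmation.** The word is attached only to progression, as in section 7.1 ("Patients with confirmed progressive disease who, in the investigator's opinion, continue to receive benefit from Axitinib treatment") and section 10, item 4 ("Confirmed PD and Investigator determination that the patient is no longer benefiting from treatment with Axitinib").
- **Status.** Response rate and duration of response are secondary objectives 3 and 4 (section 3.2).

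**The concern.** Two modest thresholds joined by *or*, read on two occasions, give a patient with both measurements up to four chances to cross a line by measurement error. There is no control arm whose response rate could be subtracted. Section 9 also allows lesions seen only on physical examination to be judged by size alone, and section 5.2 admits these from 10 mm. For a single lesion of that size the PR threshold is 10% × 10 mm = 1 mm.

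At stake is the meaning of objectives 3 and 4. A response that disappears at the next scan counts the same as one that lasts. Neither section 13.4 nor 14.3 says where duration of response starts and ends. Under section 9, losing PR without meeting the progression criteria leaves the patient with stable disease. If duration runs to progression, a chance crossing could therefore accrue stable-disease time as duration.

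**Working it through.** **The plan's own figure.** The documents give no false-response rate and no measurement error for size or density. The only design calculation is for the primary endpoint, and it reproduces: with 37 patients and success at 24 or more alive, the exact one-sided error at 50% is 0.049 and power at 70% is 0.807. It does not involve response.

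**Inputs.** From the documents: PR thresholds of 10% (size) and 15% (density) joined by *or*; scans at weeks 8, 16 and 24; 37 patients. Assumed: sS and sD, the standard deviations of the percentage change between two scans in size and density when nothing has truly changed; normal errors, independent for size and density; one baseline scan shared by all follow-ups, so that two changes correlate at 0.5.

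**One scan.** P(PR) = 1 − [1 − Φ(−10/sS)] × [1 − Φ(−15/sD)]. For sS = 5% and sD = 10%: Φ(−2) = 0.0228 and Φ(−1.5) = 0.0668, so 1 − 0.9772 × 0.9332 = 0.088.

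**Two rules, by simulation (at least 1,000,000 unchanged patients per setting).** *Best of two*: PR at week 8 or week 16. *Confirmed*: PR at weeks 8 and 16, or at weeks 16 and 24.

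| sS / sD | One scan | Best of two | Confirmed |
|---|---|---|---|
| 3% / 5% | 0.2% | 0.3% | <0.1% |
| 5% / 5% | 2.4% | 4.4% | 0.7% |
| 5% / 7.5% | 4.5% | 8.1% | 1.5% |
| 5% / 10% | 8.8% | 15.2% | 3.8% |
| 7% / 10% | 13.8% | 23.1% | 6.9% |
| 10% / 10% | 21.5% | 34.0% | 13.0% |
| 10% / 15% | 29.2% | 44.5% | 19.6% |

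If all 37 patients were unchanged, best of two would give between 37 × 0.0034 = 0.1 and 37 × 0.445 = 16.5 false responders.

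Three things follow:
- Taking the better of two scans multiplies the one-scan share by about 1.5 to 2.
- The best-of-two share passes 10% only when the standard deviation of change is about 7% or more for size, or about 10% or more for density.
- From the 5% / 5% row down, confirmation divides the best-of-two share by about 6 (4.4/0.7) to 2 (44.5/19.6).

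Requiring PR specifically at both weeks 8 and 16 gives lower figures (4.5% instead of 6.9% at 7% / 10%), but that is a stricter rule than the one proposed below.

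**Sensitivity to growth.** The table assumes no true change. With an assumed 5 points of size growth per 8 weeks, the best-of-two share falls from about 9%, 23% and 32% to about 6%, 13% and 20% at settings of 5% / 8%, 7% / 10% and 8% / 12%.

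**The case against.** The strongest reply is that the size of the problem rests wholly on assumed measurement error and that several features of the trial reduce it. Non-responding tumours often grow, the other PR conditions remove some chance crossings, and one core reads all the imaging. Patients with only non-target lesions cannot be PR, and those without density readings have only the size criterion. The share in the table applies to unchanged patients only. The Choi definition as the protocol reproduces it has no confirmation step. Confirming at week 24, about 5.5 months (24 × 7 / 30.4 days), comes after the predecessor's RECIST-based median PFS of 3.7 months, so a failed confirmation may often mean stopping or death. All of this stands. It argues against replacing the planned rate, but not against showing a confirmed rate beside it.

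A reader might also draw stronger conclusions that the documents do not support:
- *That the plan states a best-of-two rule.* Section 13.4 can also be read as a rate at each time point. The one-scan column then applies and the missing confirmation remains.
- *That the analysis demands confirmation of progression but not of response.* The phrase in section 10 governs stopping treatment. For analysis, section 8.3 dates progression at the initial event.
- *That section 1.2 admits poor imaging for this trial.* "imaging was not optimized for interpreting images with alternate radiologic criteria" describes the retrospective re-reading of the predecessor's scans.
- *That the unconfirmed rate will be used to support hypothesis 2.2.* No section links the two.

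**Conclusion.** The gap is real and small. The plan counts a Choi response without asking that it persist, and does not say clearly whether the rate is a best-of or a per-time-point figure. Some stable patients can therefore be counted as responders, but a reader should not infer that a large share will be. Under the model above that share is anywhere from 0.3% to about 45% of truly unchanged patients by best of two scans, and from under 0.1% to about 20% with confirmation on consecutive scans. The documents contain nothing that narrows either range.

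The result rests on normal, independent errors, a shared baseline and no true change; growth, the other PR conditions and central reading push it down. It is not an estimate of bias in the overall response rate. The endpoint is secondary and descriptive, and the 6-month survival test is untouched.

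**What to change.** In section 13.4, keep the planned response rate and state whether it is the best of weeks 8 and 16 or a rate at each time point. Then add:

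*The rate of confirmed response (CR or PR still met at the next scheduled 8-week scan) and the duration of confirmed response will be reported beside the unconfirmed rate and duration, with exact 95% CIs for the rates; responders with no later scan will be counted as unconfirmed and their number shown.*

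The same paragraph should say from which scan and to which event duration of response is measured.

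The cost is wording only. A response first seen at week 16 is checked at the week-24 scan already in the schedule. The downside is that the confirmed rate is lower and misses true responders who die or stop before the next scan, which is why both rates are shown. Keeping the unconfirmed rate also preserves comparison with the predecessor's Choi figure.
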